4.2. Safety Endpoints

The safety endpoints are:

- Adverse events.
- Laboratory assessment
 - Hematology
 - Chemistry
- Vital signs
- ECG results
- Concomitant medications

4.3. Pharmacokinetic and Pharmacodynamic Evaluations

None planned.

5. TRIAL CONDUCT CONSIDERATIONS

5.1. Changes in Inclusion and Exclusion Criteria

No changes are planned.

5.2. Interim Analysis and Early Stopping

None planned.

5.3. Sample Size Adjustment

Not applicable.

6. DATA ANALYSIS CONSIDERATIONS

6.1. General Considerations

The overall goal of the study is to obtain estimates of effect size for efficacy and safety endpoints that will be used to inform the design of future studies. As stated in the protocol, this study will be analyzed without specific statistical criteria. That is, no formal statistical hypothesis testing will be conducted and consequently a level of significance (α level) is not specified in this Statistical Analysis Plan. There will be statistical testing with P values and confidence intervals computed. The P values will be interpreted as an assessment of consistency with the play of chance (small P values indicating a small likelihood the observed effect is due to chance) and will be used qualitatively in decisions concerning next steps.

Statistical analyses will be performed at the conclusion of the study once all data have been collected, cleaned, and the database has been locked.

Medical history events and adverse events will be coded to standard “preferred terms” and “system organ classifications (SOC)” using the Medical Dictionary for Regulatory Activities (MedDRA) Version 21.0.

Concomitant medications will be coded using the World Health Organization Drug Dictionary (WHODRUG) Version Sep-2017 B2.

All statistical programming will be done using SAS[®] version 9.4 (SAS[®] Institute, Cary, North Carolina). All tables, figures and listings will be produced in landscape format.

In general, all data will be listed by treatment arm, subject and visit/time point where appropriate. The summary tables will have columns corresponding to, or be stratified by, treatment arm. The 6 treatment arms are: 1.5 mg Cytisine – Commercial Schedule, 3.0 mg Cytisine – Commercial Schedule, Placebo – Commercial Schedule and 1.5 mg Cytisine – tid Schedule, 3.0 mg Cytisine – tid Schedule, Placebo – tid Schedule.

The total number of subjects under the stated analysis set in each treatment arm (N) will be displayed in the header of summary tables.

Data will be summarized using descriptive statistics for continuous variables. Unless otherwise specified, descriptive statistics will include number of subjects, mean, standard deviation, minimum, median and maximum. In case of $n < 2$, where n indicates the number of evaluable subjects at the particular time point, the standard deviation will be empty. The statistic “Missing” will also be presented as the number of missing entries/subjects, if any at that visit/timepoint, and presented as a summary statistic only when non-zero. The minimum and maximum statistics will be presented to the same number of decimal places as the original data. The mean and median will be presented to one more decimal place than the original data, whereas the standard deviation will be presented to two more decimal places than the original data.

In summary tables of categorical variables, counts and percentages will be used. The count [n] indicates the actual number of subjects with a particular value of a variable or event, which should always be less than or equal to the total number of subjects with non-missing value of the variable or event [M]. Percentage will be obtained by: $\% = (n/M) * 100$. Unless otherwise stated, all percentages will be expressed to one decimal place.

In by-visit summary tables only scheduled visits/timepoints will be summarized. In listings all visits and timepoints with any data collected, including both scheduled and unscheduled ones, will be included.

All dates in tables, figures and listings will be displayed in DDMMYY format.

All outputs will be sent to Achieve as electronic files in RTF format documents.

6.2. Definition of Analysis Timepoints

- **Baseline:** The last non-missing observation prior to the first dose of study drug (cytisine and/or placebo), unless otherwise specified. If both a planned assessment and repeat assessment (e.g., retest) meet the above criteria and were collected on the same date and time, the repeat assessment will be used as baseline.
- **Change from Baseline:** The change from baseline values will be derived for each subject as the post-baseline value minus the baseline value.
- **Pre-treatment Period:** Prior to first dose of study drug on Day 1.
- **Study Treatment Period:** Starts on the date of the first dose of study drug (Day 1), continues through the last dose of study drug (Day 25) and ends on the date of the Week 4 (Day 27 EOT) visit.
- **Smoking Cessation Period:** Includes the weekly visits at Week 5, Week 6, Week 7, and Week 8.
- **Follow-up Period:** Includes the weekly visits at Week 5, Week 6, Week 7, and Week 8.

- **Study Day:** Study day will be calculated for safety endpoints relative to the first dose of study drug (cytisine and/or placebo). The first dose of study treatment will be Day 1, and the date preceding Day 1 will be Day –1 which is consistent with the Submission Data Standards (Version 3.1) from Clinical Data Interchange Standards Consortium (CDISC).

6.3. Data Handling Rules

Dropouts (ICH E3/11.4.2.2) will not be replaced during the study, but will be included in the data analysis to the extent that evaluable data are present.

For qualitative parameters, a category with the number of subjects with missing values will be presented where applicable.

6.3.1. Missing Dates

Partial or missing dates will be imputed only if a date is required to derive a study endpoint (e.g. time to failure, duration of AE). Otherwise no date imputation will be done. Date imputation will follow the rules below.

Efficacy Related Dates

Partial or missing dates required to computing efficacy endpoints will be imputed as follows:

- **Missing day only:** For partial dates with only the day of the month missing, the day will be imputed as the 15th day of the month, provided that a preceding date of interest does not occur in the same month. If the preceding date does occur in the same month, then the missing day will be imputed as half the distance between the preceding date and the end of the month.
- **Missing month and day:** For partial dates with the month and day missing, the month and day will be imputed as July 1st, provided that a preceding date of interest does not occur in the same year. If the preceding date occurs in the same year, then the month and day will be imputed as half the distance from the preceding date to the end of the known year.
- **Missing month, day, and year:** Missing dates will be imputed as the date of first dose.
- **In situations where the above rules result in an illogical time (e.g., negative study day, negative time to failure, etc) the date will be imputed as the date half the distance between the preceding date of interest and the partial date.**

Safety Related Dates

For safety data where the date of onset is during or after administration of the first dose of study drug, missing or partial start dates will be imputed as the earliest possible date that is on or after the date of the first dose of study drug. For events occurring prior to first dose of study drug, missing or partial dates will not be imputed.

- Missing day only: If the start date and date of first dose share the same month and year, the missing start day will be imputed as the day of first dose. If the start date month is after the month of first dose, day will be imputed as the 1st (i.e., 01-Jan-2019).
- Missing month and day: If the start date and date of first dose share the same year, day and month will be imputed as the day and month of first dose. If the start date year is after the year of first dose, the month and day will be imputed as January 1st (i.e., 01-Jan-2019).
- Missing month, day, and year: Missing start dates will be imputed as the date of first dose.

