All randomized subjects will initiate study treatment the day after randomization, receive 25 days of treatment and then be followed for up to 8 weeks post-randomization (approximately 31 days post-treatment). Therefore, the duration of the study will be approximately 8 weeks post-randomization for each subject.

Study Procedures:

Prior to taking part in the trial, subjects will be provided with an informed consent document outlining study requirements and procedures. Subjects will be given adequate time to review, discuss, and decide whether they wish to participate.

Subjects providing signed informed consent will be assessed during the Screening Period to determine their eligibility for the trial. If eligible, subjects will be required to attend a clinic visit prior to randomization in order to establish a quit date that will in turn determine the date of randomization. The quit date must be 5-7 days after starting treatment and treatment must begin on the day after randomization. Subjects will be randomized 2:1 (active vs. placebo) in a blinded manner to either Arm A or Arm B, versus Arm C and similarly to either Arm D or Arm E versus Arm F. Subjects will be provided with smoking cessation counseling beginning on the clinic visit during screening prior to randomization (setting quit date and plan), again on day of randomization, and continuing at various scheduled times through the Week 8 Follow-Up Period.

Compliance will be assessed during the treatment period by reviewing subject's diary (date and time of dosing) as well as ongoing drug accountability at each clinic visit (Days 2, 3, 6, 12, 16, 20, and 27).

Subjects will be assessed for efficacy (number of cigarettes smoked daily during treatment as well as smoking cessation status by self-report of abstinence with biochemical verification (expired CO) during the follow-up assessments at Week 5, 6, 7 and 8).

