7. STUDY DESIGN OVERVIEW

7.1. Study Design

This will be a six-arm, multi-center, double-blind, randomized, placebo-controlled, Phase 2b study conducted in male or female adults ≥ 18 years of age, smoking 10+ cigarettes daily, and willing to set a quit date that is 5-7 days after being randomized on the study. The study will be double-blinded to dose but not to the administration schedule. Study treatment must start the day after randomization such that study treatment is initiated prior to the quit date.

Subjects must meet all inclusion and exclusion criteria. Subjects will be stratified at randomization by BMI class (18.5 to <25 kg/m²; 25 to <30 kg/m²; 30 to <35 kg/m²). A total of approximately 250 subjects will be randomized 2:1 in a blinded manner to either Arm A or Arm B, vs Arm C (2:1 randomization) or Arm D or Arm E vs Arm F (2:1 randomization) as shown in Figure 2.

Figure 2: Study Design Overview

The study will be comprised of a pre-study screen, followed by twenty-five (25) days of study treatment, and post-treatment follow up visits to Week 8 post-randomization.

Each subject will receive twenty-five (25) days treatment either using the commercial titration schedule (i.e. decreasing daily tablets over the 25 days) or a simplified (tid) schedule during the Treatment Period. Smoking assessments will occur daily during the Treatment Period via self-reported cigarette count (number cigarettes smoked in the past 24 hours). Smoking abstinence

will be further assessed during the Follow-up Period starting after the Day 27±2 (Week 4) visit and documented through Week 5 (±3 days), Week 6 (±3 days), Week 7 (±3 days) and Week 8 (±3 days) post-randomization. Safety reporting will begin at randomization and continue through the Week 8 visit. The end of the study is defined as the last Week 8 visit for the last subject. Treatment assignment unblinding for subjects will not occur until the end of the study has been reached, the database has been locked, and final study analyses have been performed, unless defined as an unblinding exception in Section 7.3.4.

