2. STUDY DESCRIPTION

2.1. Study Design

This Phase 2b study is a six-arm, multicenter, randomized, double-blind, placebo-controlled, and parallel-design trial of the safety and efficacy of cytisine in adult cigarette smokers who are willing to set a quit date that is 5-7 days after being randomized on the study. A total of 250 subjects are planned to be randomized at the ratio 2:1 to cytisine treatment and the respective placebo treatment as designated by the protocol defined schedule (i.e. the commercial titrated schedule vs the simplified three times daily (tid) schedule) for 25 days. Subjects will be stratified at randomization based on BMI class (18.5 to <25 kg/m²; 25 to <30 kg/m²; 30 to <35 kg/m²) as defined in the protocol. The six treatment arms will be:

Figure 1: Study Design Overview

The study will be comprised of a pre-study screen, followed by twenty-five (25) days of study treatment, an end-of-treatment visit at Week 4 (Day 27 ± 2 days), and weekly post-treatment follow up visits from Week 5 to Week 8 post-randomization.

Blinding

- The study will be double-blinded to dose (1.5 mg cytisine, 3.0 mg cytisine, placebo) but not to the administration schedule (commercial titration schedule, simplified tid schedule).
- Sponsor and contract research personnel responsible for collecting, monitoring and analyzing the study data will also be blinded to dose but not to administration schedule.
- In order to blind the study treatment dose, all subjects will take 2 tablets at every scheduled dosing. Subjects randomly assigned to Arm A or Arm D will take one 1.5 mg cytisine tablet and one placebo tablet at each dosing. Arm B or Arm E subjects will take two 1.5 mg cytisine tablets at each dosing. Arm C and Arm F subjects will receive two placebo tablets at each daily scheduled dosing to correspond to cytisine dosing.

Randomization

- Eligible subjects will be randomized 2:1 in a blinded manner to either Arm A or Arm B vs Arm C (2:1 randomization) or Arm D or Arm E vs Arm F (2:1 randomization)

- Subjects will be stratified at randomization by BMI class (18.5 to <25 kg/m²; 25 to <30 kg/m²; 30 to <35 kg/m²).
- Unique subject number and randomization code will be assigned to each study subject
- Parallel group design

Multicenter Trial

- This study will be conducted at multiple sites across the US

Type of Comparison

- Superiority in favor of cytisine

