7-day point prevalence is a binary endpoint (success, failure) at each of the following visits: Week 5, Week 6, Week 7 and Week 8. At each visit, success is defined for a subject as having reported not smoking any cigarettes over the past 7 days with biochemical verification by an expired-air CO reading <10 ppm. Any other outcome will be regarded as a failure. All subjects will have a realization of this endpoint, thereby enabling analyses that follow the ITT principle without imputation.

Time to failure to maintain abstinence through Week 8 will be evaluated for the subgroup of subjects who were classified as a success for the initial quit rate endpoint (see previous definition). Time to failure to maintain abstinence (days) will be calculated as end date of abstinence minus start date of abstinence + 1. The start date of abstinence will be defined as the date of the Week 4 (Day 27 EOT) visit. The end date of abstinence will be defined as the earliest date that the subject was known to have resumed smoking. Specifically:

- At a visit, if a subject reported not smoking in the past 7 days but has smoked since the last visit (either by the subject's self-report or $CO \geq 10$ ppm), the end date of abstinence will be the date of that last visit.
- At a visit, if a subject reported not smoking since the last visit but has smoked in the past 7 days (either by the subject's self-report or $CO \geq 10$ ppm), the end date of abstinence will be defined as the date of the visit minus 7 days.
- Subjects who have not resumed smoking at the final (Week 8) visit will have end date of abstinence censored at the date of the Week 8 visit.

Relationship between Outcome Variables and Smoking Reduction and Cessation

Endpoints: The relationships between subject-reported outcomes (e.g. anxiety, depression, withdrawal symptoms, tobacco craving, alcohol use) and the following smoking efficacy endpoints will be evaluated:

- The primary efficacy endpoint, which measures reduction in smoking during the study treatment period.
- Initial quit rate, which evaluates smoking cessation at Week 4 (Day 27/EOT).

- Abstinence from Week 5 to Week 8.

It is expected that the relationship between each of these efficacy variables and the following subject-reported outcome variables will be evaluated for this objective:

- Change during the treatment period, in self-reported number of cigarettes smoked over the previous 24 hours.

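### The SAP's imputation rules for missing efficacy dates can give negative or overlong times to failure, for an endpoint whose true range is about 1 to 35 days

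*SAP*

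**What the plan says.** SAP 4.1.2 defines the endpoint for subjects who succeeded on the initial quit rate: "Time to failure to maintain abstinence (days) will be calculated as end date of abstinence minus start date of abstinence + 1". It adds: "The start date of abstinence will be defined as the date of the Week 4 (Day 27 EOT) visit". The end date is built from clinic visits. It is either the date of the previous visit or the visit date less seven days, depending on what the subject reports. A subject still abstinent at the end is censored at the Week 8 visit.

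The EOT visit is on Day 27, give or take two days (SAP 2.1). Protocol 7.1 sets the last assessment at "Week 8 (±3 days) post-randomization". First dose is Day 1, the day after randomization.

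SAP 6.3.1 names time to failure as an endpoint that may need imputed dates. Its efficacy rules are:
- Day missing: the 15th of the month, or halfway to month end if a preceding date of interest lies in that month.
- Month and day missing: 1 July by default. Where an earlier date of interest shares the calendar year, a different rule applies: "the month and day will be imputed as half the distance from the preceding date to the end of the known year".
- Whole date missing: "Missing dates will be imputed as the date of first dose".
- If the result is illogical, with negative time to failure given as an example: "the date will be imputed as the date half the distance between the preceding date of interest and the partial date".

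None of these rules refers to the visit schedule or caps the imputed date at Week 8.

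**The concern.** The rules suit a study in which events may fall anywhere in a calendar year. Here the whole interval from EOT to Week 8 is about a month, and each attended visit has a nominal date. A rule that sends a date to first dose puts the end of abstinence before its start. A rule that sends it towards mid-year puts it months after the study has ended.

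SAP 10.2.5 reports the minimum, maximum and median time to failure by arm, with Kaplan-Meier plots, among initial quitters only. These are a subset of arms of 50 active or 25 placebo subjects. One overlong value becomes the arm's maximum and stretches the plot. One negative value becomes the minimum or has to be dropped.

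**Working it through.** **Inputs.** EOT Day 25 to 29, nominal 27 (SAP 2.1). Week 8 is Day 56 ± 3 (Protocol 7.1). First dose is Day 1. Time to failure = end − start + 1 (SAP 4.1.2). Calendar dates of visits are not in the documents. I assume EOT dates between 15 October 2018 and 1 May 2019, a range lying between the date of protocol version 2.0 (26 September 2018) and that of SAP version 2.0 (29 May 2019).

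**The plan's own figure.** The protocol synopsis gives about 31 days of follow-up after treatment: 8 × 7 − 25 = 31. This reproduces.

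**True range.** Nominal maximum 56 − 27 + 1 = 30 days. At the window extremes it is 59 − 25 + 1 = 35 days.

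**Whole date missing.** The end date becomes Day 1. Time = 1 − 27 + 1 = −25; with EOT on Day 25 it is −23 and on Day 29 it is −27. It is always negative, whatever the calendar date.

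**Repair of that result.** The rule takes a midpoint with a partial date, and a wholly missing date supplies none, so strictly the rule is undefined. Using the imputed first-dose date as the only candidate:
- EOT as preceding date: midpoint (27 + 1)/2 = Day 14; 14 − 27 + 1 = −12 (−11 to −13 over the EOT window).
- Week 5 or Week 6 visit as preceding date: −11.5 to −1 over the windows.
- Week 7 visit as preceding date: nominally (49 + 1)/2 = Day 25; 25 − 27 + 1 = −1. Over the windows this runs from −4.5 to +2.5, so some timings turn non-negative.

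**Month and day missing, EOT in the same year.** With EOT as preceding date, time = (days from EOT to 31 December)/2, rounded down, + 1.

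| EOT date | Days to 31 Dec | Time to failure |
|---|---|---|
| 1 Jan 2019 | 364 | 183 |
| 28 Jan 2019 | 337 | 169 |
| 1 Mar 2019 | 305 | 153 |
| 1 May 2019 | 244 | 123 |
| 15 Oct 2018 | 77 | 39 |
| 1 Nov 2018 | 60 | 31 |
| 1 Dec 2018 | 30 | 16 |

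The last EOT date giving more than 35 days is 22 October: 70/2 + 1 = 36.

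**Month and day missing, EOT in the previous year.** The date becomes 1 July 2019. EOT on 31 December 2018 gives 182 + 1 = 183 days; 15 December gives 198 + 1 = 199; 27 November gives 216 + 1 = 217. Strictly, a Week 8 visit held in window falls in 2019 only for EOT from 28 November, which gives 216.

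**If overlong times also count as illogical.** One repair only halves them: 183 becomes 92 and 123 becomes 62, still above 35.

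**A genuinely partial date that the repair does not rescue.** Take first dose 2 January 2019, Day 20 visit 21 January, Week 8 on 26 February, and EOT month and day missing. EOT is imputed at 344/2 = 172 days after 21 January, which is 12 July. In days of the year, time = 57 − 193 + 1 = −135. The repair gives 21 + 86 = day 107 (17 April), and 57 − 107 + 1 = −49.

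**Day only missing.** Results run from 1 to 49 days: never negative, but they can pass the maximum. With EOT on 26 January 2019 and Week 8 on 1 March (34 days later, true time 35), the 15 March imputation gives 48 + 1 = 49.

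**The case against.** The strongest reply is that these rules will hardly ever be used. The endpoint is built from clinic visits. Members of the subgroup must have had a carbon monoxide reading at EOT, and each follow-up visit records smoking status in clinic. Incomplete case report forms are queried (Protocol 19.2), and analysis follows cleaning and lock (SAP 6.1). An attended visit with data but no month is unlikely. This stands for attended visits. It does not cover an initial quitter who never attends Week 8. SAP 4.1.2 gives no other censoring date for that subject, so a literal reading could lead to the first-dose rule.

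The consequences are also limited. The 169 days for an undated Week 8 visit is a censoring time of a subject still abstinent. Moving it from day 30 to day 169 leaves the Kaplan-Meier estimate unchanged at every event up to day 30; the reported maximum and the axis change. Time to failure is not among the key endpoints in SAP 6.5, and SAP 10.2.5 specifies no between-arm test for it.

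A reader might infer two stronger statements that the documents do not support. One is that the rules yield about 170 days as a fixed property. That figure needs an EOT date in late January, which is an assumption. The other is that the repair always leaves a negative time negative. With a Week 7 visit as the preceding date it need not, and for a wholly missing date the rule is, strictly, undefined.

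**Conclusion.** The efficacy-date rules do not fit this endpoint. That the first-dose rule gives a negative time (−23 to −27 days) needs no calendar assumption. The repair is either undefined there or usually leaves the time negative. The overlong values, about 120 to 217 days against a true maximum of 35, rest on assumed EOT dates from late November (with the missing date in the following year) to 1 May.

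This is a minor drafting defect. How often visit dates will be missing is not stated. The route most likely to matter is dropout before Week 8, and the SAP does not say that such subjects are to be handled by date imputation; it simply leaves no other rule. A reader should not infer that the primary endpoint is affected: it uses diary counts over Days 1 to 25 and does not depend on these dates. Nor should a reader infer that between-arm conclusions would change, since nothing in the documents shows that.

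**What to change.** For efficacy dates, delete the first-dose, 1 July, half-to-year-end and 15th-of-month imputations, and replace them with two rules:
1. Attended visit with a partial or missing date: impute the nominal date (first dose + 26 days for EOT; randomization + 35, 42, 49 or 56 days for Weeks 5 to 8), restricted to any known month and year and to lie between the adjacent known visit dates.
2. Visit not attended: impute no date. Censor time to failure at the last attended visit with abstinence confirmed. A nominal date would be unsuitable here, because it would credit abstinence that nobody observed.

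The cost is one SAP paragraph, to be settled before unblinding (Protocol 16), and no new data. A visit held within its window is misdated by at most two days (EOT) or three days (Weeks 5 to 8); the error is larger if the visit fell outside it. The change does not touch the separate rule that dates failure at the visit less seven days. Without any imputation, that rule can place failure before EOT: a Week 5 visit on Day 32 with EOT on Day 29 gives 25 − 29 + 1 = −3.
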